# 1. LIST OF ABBREVIATIONS AND RELEVANT DEFINITIONS

ALAT	Alanine aminotransferase
ASAT	Aspartate aminotransferase
BSID-III	Bayley scales of infant development, third edition
DSMB	Data safety monitoring board
EPO	Erythropoietin
EudraCT	European drug regulatory affairs clinical trials
GCP	Good clinical practice
γGT	Gamma-glutamyl transferase
HDFN	Hemolytic disease of the fetus and newborn
IUT	Intrauterine red cell transfusion
LDH	Lactate dehydrogenase
LUMC	Leiden University Medical Center
MDI	Mental developmental indexes
METC	Medical research ethics committee (MREC); in Dutch: medisch ethische toetsing
	commissie (METC)
PDI	Psychomotor development indexes
(S)AE	(Serious) adverse event
SUSAR	Suspected unexpected serious adverse reaction
Wbp	Personal data protection act; in Dutch: Wet bescherming persoonsgegevens
WMO	Medical research involving human subjects act; in Dutch: wet medisch-
	wetenschappelijk onderzoek met mensen

#### 2. SUMMARY

**Rationale:** neonates with hemolytic disease of the fetus and newborn (HDFN) due to red cell alloimmunization often require top-up (red blood cell) transfusions to treat late anemia during the first 3 months of life. Late anemia in neonates with HDFN may be due to depressed erythropoiesis (hyporegenerative anemia) and/or persisting (intra-marrow) destruction of erythrocytes by remaining antibodies, which is not necessarily associated with parameters of hemolysis. Hyporegenerative anemia occurs in particular in neonates treated with intrauterine red cell transfusions (IUT) due to bone marrow suppression. Approximately 80% of infants with rhesus hemolytic disease treated with IUT require at least one top-up transfusion, with an average of two top-up transfusions per infant.

Since more than a decade erythropoletin (EPO) has been applied in small studies and casuistic reports in children with HDFN. It is controversial whether neonates with HDFN treated with or without IUT benefit from this treatment to reduce the risk of delayed anemia and subsequently, the need for top-up transfusions. Due to the lack of evidence, routine use of EPO is currently not recommended. To determine a role for EPO in patients treated with IUT, a well-designed randomized controlled clinical trial of sufficient sample size is required. **Objective**: to evaluate the effect of darbepoetin alfa on the need for top-up transfusions in neonates with HDFN due to red cell alloimmunization treated with IUT. Secondary outcomes are number of days of admission for top-up transfusions, percentage of infants with high ferritin levels and high blood pressure.

Study design: randomized controlled trial.

**Study population:** all (near)-term neonates (gestational age ≥ 35 weeks) admitted to the Leiden University Medical Center (LUMC) with HDFN, treated with IUT.

**Intervention**: treatment with darbepoetin alfa subcutaneously at a dosage of 10  $\mu$ g/kg once a week for a period of 8 weeks (intervention), or "standard care".

Main study endpoints: number of top-up transfusions required per infant.

Nature and extent of the burden and risks associated with participation, benefit and group relatedness: all infants participating in either treatment arm of the study are subjected

to routine neonatal care. Darbepoetin alfa is given subcutaneously, once a week for a period of 8 weeks on home visits. Administration of darbepoetin alfa may cause local skin reactions, increased blood pressure with rarely convulsions and hypersensitivity reactions. However, these risks are small and are observed in different populations. If effective, darbepoetin alfa prevents or reduces the amount of top-up transfusions. Additionally, darbepoetin alfa may improve neurodevelopmental outcome. No extra blood will be drawn from the infants in addition to the weekly routine measurements of complete blood counts. Blood pressure will be measured three times throughout treatment.

HDFN is a condition occurring exclusively in infants and can therefore only be studied in this specific population.

#### 3. INTRODUCTION AND RATIONALE

The mainstay of antenatal treatment of fetal anemia due to red cell alloimmunization is (serial) intrauterine red cell transfusions (IUT). The mainstay of postnatal treatment in hemolytic disease of the fetus and newborn (HDFN) is (1) intensive phototherapy and exchange transfusion to treat hyperbilirubinemia and prevent kernicterus, and (2) top-up transfusions to treat anemia. Up to 80% of infants with HDFN treated with IUT require at least one top-up transfusion for late anemia during the first 3 months of life, with an average of two top-up transfusions and therefore two hospital admissions per infant. Late anemia is attributed to two mechanisms: "hyporegenerative anemia" characterized by depressed erythropoiesis and "late anemia of hemolytic disease" caused by persisting antibodies, destroying newly produced erythrocytes. "Hyporegenerative anemia" occurs in particular in neonates treated with several IUTs due to bone marrow suppression. To distinct these two mechanisms, a persistence of a high antibody titer can be used. Several risk factors for late anemia have been reported, including serial IUT (due to bone marrow suppression), severity of HDFN, reduced use of exchange transfusions during the neonatal period and reduced survival of transfused red blood cells. Finally, erythropoietin deficiency is also considered as a possible contributing factor to late anemia. Erythropoietin (EPO) has been increasingly used in neonates to prevent or reduce neonatal anemia without short or long-term adverse effects. Several small studies and casuistic reports suggest that neonates with HDFN may benefit from treatment with EPO to reduce the risk of delayed anemia and subsequent top-up transfusions. However, other authors found that EPO may be less effective than expected. Due to the lack of evidence, routine use of EPO is currently not recommended. To determine a role for EPO in this group of patients, a well-designed randomized controlled clinical trial of sufficient sample size is required. Potentially, EPO stabilizes the hemoglobin levels of these infants and thus prevents anemia, hospital admissions for top-up transfusions and potential transfusion reactions, creating a more stable and natural postnatal course for patients with HDFN. In this scenario, the current

management of weekly out-patient visits and weekly blood draws for hemoglobin level measurements, may be reduced, further contributing to reduction of the burden for these infants.

HDFN is a condition occurring exclusively in infants and can therefore only be studied in this specific population.

# 4. OBJECTIVES

The primary objective of this study is to investigate whether darbepoetin alfa is effective in reducing the incidence of late anemia in infants with HDFN treated with IUT and therefore in decreasing the number of top-up transfusions per infant. As secondary objectives the percentage of infants that required a top-up transfusions will be assessed, as well as the time from birth to first top-up transfusion, number of days of admission for top-up transfusions, percentage of infants with a systolic blood pressure  $\geq$  2 SD above age adjusted mean systolic blood pressure and the percentage of infants with ferritin levels >200 µg/L. For exploratory purposes, the long-term neurodevelopmental outcome at 2 years of age will be assessed using the BSID-III test.

# 5. MATERIAL AND METHODS

# 5.1 Study population

All (near) term neonates (gestational age  $\geq$  35 weeks) with HDFN (due to Rhesus-D, -C, -c, -E, Kell or other red blood cell alloimmunization) treated with IUT and admitted to the Leiden University Medical Center (LUMC) between May 2017 and October 2020 are eligible for the study. The LUMC is the single national referral center in the Netherlands for pregnancies complicated by maternal red blood cell alloimmunization. Approximately 15 eligible patients are treated in the LUMC a year.

# Inclusion criteria:

- Gestational age ≥ 35 weeks.
- Treatment with IUT due to Rhesus-D, -C, -c, -E, Kell or other red blood cell alloimmunization.
- Birth at the LUMC.

Exclusion criteria:

- Gestational age <35 weeks.
- Treatment with IUT due to other causes than red blood cell alloimmunization.
- Early onset proven neonatal sepsis.
- •

[figure not shown]
# 5.2 Study design

Randomized controlled trial. Included neonates will be randomized at birth to treatment with EPO (intervention group) or "standard of care", 1:1 allocation. In the treatment group, EPO (darbepoetin alfa) is administered subcutaneously at a dosage of 10 µg/kg once a week, starting at day 7, for a period of 8 weeks. Treatment is administered during weekly home visits after discharge from the LUMC. Concomitant therapy with folate (0.25 mg/day) is given

in both groups (standard practice). Concomitant iron therapy is given if ferritin level drops below 75 microg/l. Weekly routine measurements of complete blood counts (including hemoglobin level, hematocrit and reticulocyte count) will be performed in both groups (standard practice). EPO is discontinued if hemoglobin level is  $\geq$  13 g/dL after at least 4 weeks of treatment with EPO. Blood pressure will be measured at the start of treatment, after four weeks and after eight weeks. Monthly measurements of liver enzymes (aspartate aminotransferase (ASAT), alanine aminotransferase (ALAT), gamma-glutamyl transferase ( $\gamma$ GT) and lactate dehydrogenase (LDH)) will also be performed in all groups (standard practice). In addition, the neonatal EPO-level will be determined at the start of the treatment with EPO. The number of top-up transfusions received during the first 3 months of life and hemoglobin levels prior to the top-up transfusion are recorded. After initial discharge from the LUMC, top-up transfusions are performed when hemoglobin levels fall below 7.2 g/dL or when hemoglobin is between 7.2 and 8.8 g/dL if clinical symptoms of anemia (lethargy, feeding difficulties or failure to thrive) are present.

At two years of age a physical and neurological examination and an assessment of cognitive and neurological development using the Dutch version of the Bayley Scales of Infant Development, third edition (BSID-III) will be performed (standard practice). BSID-III scores provide mental developmental indexes (MDI) and psychomotor development indexes (PDI).

[figure not shown]
#### 5.3 Flow chart

[figure not shown]
# 5.4 Sample size calculation

Based on the (scarce) results in the literature, we expect a 50% reduction in the median number of top-up transfusions per patient with EPO treatment, from a median of 2 to 1. For sample size calculation we hypothesized a shift in the distribution of number of transfusions per infant as depicted in Figure 1. The distribution in the 'care as usual' group are based on data from 2000-2014. Based on these expected frequencies, group sample sizes of 21 achieve 81% power to detect a difference of 1,1 between the null hypothesis that both group means are 1,9 and the alternative hypothesis that the mean of the EPO group is 0,8 with estimated group standard deviations of 1,5 and 0,9 and with a significance level (alpha) of 0,05 using a two-sided Mann-Whitney test. The drop-out percentage is estimated at 5%,

adding (42/0.95 = 44) 1 person to each group's sample size.

#### hypothesized distribution

# 5.5 End points

Primary end points:

• Number of top-up transfusions required per infant up to 3 months of life.

# Secondary end points:

- The percentage of infants requiring a top-up transfusion up to 3 months of life;
- Time form birth to first top-up transfusion (days);
- Number of days of admission for top-up transfusions;
- The percentage of infants with a systolic blood pressure ≥ 2 SD above age adjusted mean systolic blood pressure during treatment;
- The percentage of infants with ferritin levels >200 µg/L during treatment;

Exploratory end point:

Long-term neurodevelopmental outcome at 2 years of age using the BSID-III test.

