#### 5.10 Statistical analysis

Both intention to treat and per protocol analysis will be carried out to study the differences in outcome measures between the intervention and control group. Intention to treat analysis is our primary choice of analysis. A minimal treatment with 5 out of 8 darbepoetin injections is defined as acceptable protocol deviation. A p-value < 0.05 will be considered to indicate statistical significance. The number of top-up transfusions per infant and, the number of days of admission for top-up transfusions will be compared between both groups using a Mann-Whitney U test. The time from birth to top-up transfusion will be compared between both groups using survival analysis and a log rank test. The percentage of infants requiring a top-up transfusion up to 2 months of life, the percentage of infants with a high blood pressure and the percentage of infants with high ferritin levels will be compared between both groups using  $\chi^2$  tests. If despite randomization the groups differ at baseline in type of alloimmunization, EPO-levels at birth or treatment with exchange transfusion, a multivariable model may be used in a secondary analysis to correct for these factors.

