##### *Secondary end points:*

[figure not shown]
- Number of postnatal transfusions per infant  $\geq 7$  days up to 3 months of life.
- The percentage of infants requiring a postnatal transfusion up to 3 months of life;
- Time from birth to first postnatal transfusion (days);
- Hemoglobin level at first postnatal transfusion (g/dl);
- Number of days of hospitalization and readmission(s) associated with erythrocyte transfusion(s);
- Course of hemoglobin up to 3 months of life.

*Safety end points:*

- The percentage of infants with a systolic blood pressure  $\geq 2$  SD above age adjusted mean systolic blood pressure during treatment;
- The percentage of infants with ferritin levels  $>200$   $\mu\text{g/L}$  during treatment.

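### Blood pressure is planned only as a count of infants at or above 2 SD; with about 22 infants per arm that discards most of the information, so an age-adjusted SD-score estimate should be added beside it

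*Protocol*

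**What the plan says.** The Protocol Summary lists "increased blood pressure with rarely convulsions and hypersensitivity reactions" among the possible effects of darbepoetin, and Protocol 7.3 and 7.4 repeat the risk.

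- **Readings.** Protocol 5.2: "Blood pressure will be measured at the start of treatment, after four weeks and after eight weeks". Protocol 6.3 gives the same schedule. Neither section says whether controls are measured. SAP 4.2 states the three readings for EPO-treated infants only.
- **Endpoint.** Protocol 5.5: "The percentage of infants with a systolic blood pressure ≥ 2 SD above age adjusted mean systolic blood pressure during treatment". SAP 4.3 moves it to the safety end points and keeps the threshold: "SD above age adjusted mean systolic blood pressure during treatment". SAP Table 2 has a single n (%) row for it.
- **Analysis.** Protocol 5.10 compares "the percentage of infants with a high blood pressure" between the two groups by a chi-square test, under the general rule "A p-value < 0.05 will be considered to indicate statistical significance". SAP 5.2 names no blood-pressure test.

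Neither document plans a mean, an SD score or a change from onset for blood pressure. Haemoglobin, by contrast, is analysed on its continuous scale with a linear mixed model (SAP 5.2).

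**The concern.** A count at 2 SD uses only the upper tail. If untreated infants follow the age reference, about one infant per arm is expected above the line. A moderate rise in every treated infant moves that count by only one or two, so a low percentage says little about whether the drug shifted blood pressure. The scheduled readings hold more information than the plan extracts from them. What is at stake is the precision of the statement the trial can make about a recognised risk.

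**Working it through.** **1. The plan's own power figure.** Protocol 5.4 says "group sample sizes of 21 achieve 81% power to detect a difference of 1,1", "using a two-sided Mann-Whitney test", with SDs of 1.5 and 0.9. Pooled SD = √((1.5² + 0.9²)/2) = 1.237 and d = 1.1/1.237 = 0.889. By the normal approximation z = 0.889 × √(21/2) − 1.96 = 0.92, which gives 82.2%. Applying the Mann-Whitney efficiency of 0.955 gives 80.4%; a t-based calculation gives 80.3%. The stated 81% reproduces. Then 42/0.95 = 44.2, taken as 44, or 22 per arm. This covers the primary endpoint only. No power or detectable difference is stated for blood pressure.

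**2. Assumptions not in the documents.** Untreated SD scores are N(0,1). The drug adds a shift s at weeks 4 and 8. Correlation ρ between readings is 0.3 to 0.7. Readings are complete in both arms, with 22 per arm and two-sided alpha of 0.05.

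**3. One reading per infant.** P(at or above 2 SD) = 1 − Φ(2 − s).

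| Shift | Control vs EPO above 2 SD | Chi-square power (exact enumeration) | SD score, two-sample t |
|---|---|---|---|
| +0.5 | 2.3% vs 6.7% | 3.5% | 37% |
| +0.75 | 2.3% vs 10.6% | 13% | 68% |
| +1 | 2.3% vs 15.9% | 32% | 90% |

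For 80% power at +1 SD the count needs 69 per arm and the score 16 (ratio 4.3). At +0.5 SD it is 345 against 63 (ratio 5.5).

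**4. Both on-treatment readings.** The count is any of the week-4 and week-8 readings at or above 2 SD. The expected number per arm without drug effect is 22 × 0.038 to 22 × 0.044, or 0.8 to 1.0. At +0.5 SD it is 22 × 0.105 to 22 × 0.122, or 2.3 to 2.7. With no control above the line, the chi-square test needs at least 4 of 22 EPO infants above it; with one control above, it needs 6.

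For the ANCOVA, the residual variance of the two-reading mean given onset is v = (1 + ρ)/2 − ρ², which is 0.56, 0.50 and 0.36 for ρ = 0.3, 0.5 and 0.7. SE = √(2v/22). For ρ = 0.5 and s = 0.5, SE = √(1/22) = 0.213 and s/SE = 2.35, giving power of about 63%.

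| Shift | Chi-square, any of two readings | Onset-adjusted ANCOVA |
|---|---|---|
| +0.5 | about 9-13% | about 56-77% |
| +0.75 | 26-32% | 90-98% |
| +1 | 51-60% | 99% or more |

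The ranges span ρ and combine calculation with simulation. At +0.5 SD, enumeration gives 9-12% and simulation 10-13% for the chi-square; for ANCOVA, formula gives 58-77% and simulation 56-77%. Counting the onset reading as well lowers the chi-square to 9-12%, 22-27% and 44-52%. Averaging the two readings without adjusting for onset gives 42-52%, 75-85% and 94-98%.

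**5. Precision.** An observed 1 of 22 (4.5%) has an exact 95% CI of 0.1% to 22.8%.

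**6. If only EPO infants are measured.** Neither column in step 4 can be computed. What remains is the change from onset, with variance (1 + ρ)/2 + 1 − 2ρ = 1.05, 0.75 and 0.45, so the 95% CI half-width is about 0.30 to 0.45 SD. This change is uncontrolled. With no drug effect but an assumed 0.3 SD drift in how well the age reference fits, a paired t test rejects 26-52% of the time. The same drift moves the expected count only from about 0.8-1.0 to 1.6-1.8 infants.

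**The case against.** The strongest reply is that 2 SD is a sensible safety threshold. It identifies individual infants with high pressure, adverse events also go to the DSMB, and the trial was never powered for safety outcomes. That is fair, and it is why the percentage should stay. It does not answer the point that the count says little about how far pressure moved.

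Several stronger readings are tempting, and the documents do not support them:

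- **That the SD score would detect a real rise.** At +0.5 SD the ANCOVA power is below 80% throughout the range. SAP 4.2 stops EPO at haemoglobin of 13 g/dL or more after at least four weeks, so some week-8 readings may be off drug. If the shift is present at week 4 only, the mean shift halves and paired-change power at +0.5 SD is 19-39%.
- **That the count is blind to any rise.** At +1 SD the chi-square reaches 51-60%.
- **That the point is the same with or without controls.** It is not. The chi-square comparison stands only in Protocol 5.10, and the SAP reads as a descriptive percentage in treated infants. A change from onset in one arm cannot separate drug from age, device or setting. Later doses are given at home visits, so the setting may differ from onset.
- **That the trial would conclude darbepoetin does not raise blood pressure.** Neither document says so.
- **That the SD score must already exist for every infant.** A table of upper limits by age could classify infants without it, and no reference is named.

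**Conclusion.** The point holds as a cheap gain in precision. The 2 SD count is the only planned blood-pressure analysis, and for moderate rises it uses a small part of the information in the readings: about 9-13% power against 56-77% at +0.5 SD, and 26-32% against 90-98% at +0.75 SD. These figures rest on normal SD scores that match the reference, ρ of 0.3 to 0.7, complete readings, controls measured at matching ages and the full rise at both visits. If untreated infants with this disease do not follow the reference, the percentages change. If controls are not measured, the between-arm comparison falls away. The SD score then gives only a descriptive estimate, and it should not become the main safety test.

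**What to change.** 1. Reconcile Protocol 5.10, which compares the percentage between both groups, with SAP 4.2, which states readings for EPO-treated infants only. Say whether control readings exist and at what ages.
2. Keep the percentage at or above 2 SD as the threshold safety summary, with an exact 95% CI. State which readings count and name the age reference.
3. Add to SAP 5.2 and Table 2 the age-adjusted systolic SD score at weeks 4 and 8. Where control readings exist at matching ages, give the between-arm difference adjusted for the onset value, with 95% CI. Otherwise give the mean change from onset in EPO infants with 95% CI, labelled descriptive and uncontrolled and not interpreted as a drug effect.

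The cost is SAP wording and one table row, with no new reading in any infant already measured. The downside is that the EPO-only change is more sensitive than the threshold count to a poorly fitting age reference and to a change of setting between onset and later readings.

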#### 5.6 Randomization, blinding and treatment allocation

Prior to randomization, informed consent will be obtained from parents or caregivers. Information will be given antenatal if possible to allow sufficient time to consider participation. Informed consent can also be obtained after birth, but not after the first week of life as not to interfere with the possible darbepoetin treatment schedule. If parents or caregivers agree to participate, treatment will be allocated by the web based randomization service of GRP validated program CASTORto obtain an unique trial number and assignment of treatment policy. As the primary objectives are based on hemoglobin levels (need for top-up transfusion) that are set out in a transfusion protocol, blinding or the use of placebo is not necessary. Due to the subcutaneous administration route, the use of a placebo is considered unethical.

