#### 7.4 Summary of known and potential risks and benefits

Darbepoetin alfa is registered as treatment of symptomatic anemia due to chronic kidney disease. As such, it is known that darbepoetin potentially causes local skin reactions, increased blood pressure with rarely convulsions and hypersensitivity reactions. Despite these potential risks, darbepoetin alfa can increase hemoglobulin levels and thereby prevent or reduce the amount of top-up transfusions. Potential adverse effects of transfusions would be avoided and the number of days of hospitalization could be reduced. EPO may have an additional beneficial effect on long-term neurodevelopment.

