#### 4.2 Study design

Randomized controlled trial without placebo. Included neonates will be randomized at birth to treatment with EPO (intervention group) or “standard care”, with 1:1 allocation, to be randomized in varying blocks of 4 and 6, no stratification is applied. In the treatment group, EPO (darbepoetin alfa) is administered subcutaneously at a dosage of 10  $\mu\text{g}/\text{kg}$  once a week, starting at approximately day 7, for a period of 8 weeks. Treatment is administered during weekly home visits in the treatment arm after discharge from the LUMC. Concomitant therapy with folate (0.25 mg/day) is given in both groups (standard practice). Concomitant iron therapy is given if ferritin level drops below 75 microg/l (standard practice). Weekly routine measurements of complete blood counts (including hemoglobin level, hematocrit and reticulocyte count) will be performed in both groups (standard practice). EPO is discontinued if hemoglobin level is  $\geq$  13 g/dL after at least 4 weeks of treatment with EPO. In EPO treated infants, blood pressure will be measured for safety reasons at onset of treatment, after four weeks and eight weeks. Monthly measurements of liver enzymes (aspartate aminotransferase (ASAT), alanine aminotransferase (ALAT), gamma-glutamyl transferase ( $\gamma$ GT) and lactate dehydrogenase (LDH)) will also be performed in all groups (standard practice). In addition, the neonatal EPO-level will be determined at birth in both groups. The number of postnatal transfusions received during the first 3 months of life and hemoglobin levels prior to the postnatal transfusion are recorded. After initial discharge from the LUMC, postnatal transfusions are recommended to be performed when hemoglobin levels fall below aforementioned cut-off values of hemoglobin.

Because of these clearly defined guideline and hemoglobin measures, blinding of caregivers to treatment allocation and use of a placebo was not deemed necessary.

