Collected data, including history of pregnancy, neonatal clinical records from the initial hospitalization at the LUMC and records from additional admissions and outpatient clinic visits in other hospitals than the LUMC, were collected for each included patient with written consent of parents or caregivers. Data was upon collection blinded and entered into an online secured database (CASTOR) by a member of the research team with in this database blinding of treatment allocation. The datamanager and statistician involved are blinded as well. After all data have been collected and entered in the database, and after data cleaning and finalization of the statistical analysis plan, the database will be locked and the data will be unblinded to all parties involved.

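### The reason given for not blinding does not cover the exploratory 2-year examination and BSID-III, and nothing keeps allocation from the 2-year examiner

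*Protocol*

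**What the plan says.** Protocol 5.6 gives its ground in one clause, "As the primary objectives are based on hemoglobin levels (need for top-up transfusion) that are set out in a transfusion protocol", and concludes that "blinding or the use of placebo is not necessary". It adds that a placebo would be unethical because of the subcutaneous route. SAP 4.2 gives the same ground: "Because of these clearly defined guideline and hemoglobin measures, blinding of caregivers to treatment allocation and use of a placebo was not deemed necessary".

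Protocol 5.2 also plans, "At two years of age a physical and neurological examination and an assessment of cognitive and neurological development", using the BSID-III. Protocol 5.5 lists this as the exploratory end point: "Long-term neurodevelopmental outcome at 2 years of age using the BSID-III test". Section 4 agrees that it is exploratory, while section 7.1 calls neurodevelopment a secondary end point. Section 7.4 states the expected direction: "EPO may have an additional beneficial effect on long-term neurodevelopment". The Summary makes a similar statement.

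SAP 4.2 describes the masking that does exist. Allocation is hidden in the database and from the data manager and statistician. After data collection, cleaning and completion of the SAP, "the database will be locked and the data will be unblinded to all parties involved". Neither document says who performs the 2-year assessment or whether that person is unaware of the allocation.

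**The concern.** An open-label design is easier to defend when a laboratory threshold largely decides the outcome. A neurological examination and a developmental test have no such threshold; someone judges what the child does. If that person knows the allocation and has read that the drug may help neurodevelopment, scores can drift in the expected direction.

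The documents plan no other measure of the neurodevelopmental benefit that the protocol puts forward. A favorable difference could then be partly drug and partly expectation, and the data would give no way to separate the two. The visit falls long after treatment: weekly dosing from about day 7 for 8 weeks ends at about 2 months of age, so some 22 months pass before it. Withholding allocation from an examiner at that distance is a modest request.

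**Working it through.** **Does the waiver cover the 2-year assessment?**

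- *Ground for the waiver.* Protocol 5.6 refers to the primary objectives and the hemoglobin-based transfusion protocol. SAP 4.2 refers to the transfusion guideline and hemoglobin measures.
- *What is assessed at 2 years.* A physical and neurological examination and the BSID-III. No hemoglobin rule determines either, so the ground does not reach them.
- *The placebo argument.* It explains why families and treating staff know the allocation. It does not prevent withholding it from a later examiner.
- *Existing masking.* Hiding allocation in the database and from the data manager and statistician protects data entry and analysis. It does not protect a score at the moment it is given.

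**When does unblinding happen?**

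- *Before the 2-year visits:* SAP 5.2 sets follow-up at 90 days, and SAP 4.3 does not list the BSID-III. Data collection for the SAP could therefore be complete, and the database locked, before the last 2-year visit.
- *After them:* SAP 4.2 unblinds only once all data are in, Protocol 10.5 ends the study at the last patient's last visit, and Protocol 11.2 counts the 2-year assessment as a visit for all participants.

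The timing is ambiguous. On either reading, nothing keeps allocation from the examiner.

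**How large could the effect be? (illustration only)**

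The documents give no power figure, effect size or test for the BSID-III. The one input taken from them is the group size in SAP 4.4: 21 + 21 = 42, and 42/0.95 = 44.2, stated as 44, or 22 per arm. The 81% power stated there concerns the transfusion count and does not bear on this point.

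Assumptions not in the documents: all 44 children assessed, a two-sided comparison of means at 0.05, no true drug effect, and a systematic scoring shift of 0.2 to 0.4 SD in favor of the EPO arm.

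- Standard error of the difference = √(2/22) = 0.302 SD.
- False-positive rate = P(|Z + shift/0.302| > 1.96).

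| Assumed shift | Shift / SE | False-positive rate |
|---|---|---|
| 0 | 0 | 5% |
| 0.2 SD | 0.66 | about 10% |
| 0.4 SD | 1.33 | about 26% |

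A noncentral t calculation with 22 per arm gives 9.9% at 0.2 SD and 18.8% at 0.33 SD, in line with the table. With fewer children assessed the inflation is slightly smaller. At 18 per arm the standard error is √(2/18) = 0.333 SD, and the range becomes about 9% (0.2/0.333 = 0.60) to 22% (0.4/0.333 = 1.20).

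Two reference values at 22 per arm: nominal significance needs an observed difference of about 1.96 × 0.302 = 0.59 SD, and 80% power needs a true difference of about (1.96 + 0.84) × 0.302, or roughly 0.84 SD.

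**The case against.** The strongest reply is that little rests on this endpoint. It is exploratory in Protocol 4 and 5.5, Protocol 5.10 assigns it no test, and the SAP neither lists it nor gives it a table row. The secondary label in 7.1 stands in product background, against the two sections that define the endpoints. This stands, and it limits the weight of the point. It also makes the false-positive figures an illustration of a test that nobody has planned, with a bias range that nothing in the documents anchors.

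A second reply is that masking may not be achievable. Parents know whether weekly home injections were given. In a single center with about 15 eligible infants a year, the usual examiner may already know the allocation. This also stands, so the fix has to be conditional and masking has to be recorded.

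A reader might infer four stronger things that the documents do not support:

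- *All blinding was dropped.* It was not. SAP 4.2 waives blinding of caregivers and keeps it for the database, data manager and statistician. Masking of the 2-year examiner is unstated, not rejected.
- *Examiners will be unblinded before the 2-year visits.* They may be; the text supports either order.
- *An unmasked difference could not be interpreted.* That goes too far. The observed difference needed for nominal significance, about 0.59 SD, lies above the top of the assumed bias range. Bias of that size would weaken such a finding, not empty it of meaning.
- *Bias has occurred.* The documents show exposure to bias only.

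**Conclusion.** The point holds as a modest, inexpensive improvement. The stated reason for not blinding does not extend to the 2-year examination and BSID-III, and neither document keeps allocation from the examiner. A between-arm neurodevelopmental difference would thus be exposed to expectation bias in a direction that the protocol itself names. The primary, secondary and safety results do not depend on it.

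The size cannot be derived from the documents. Under the stated assumptions, the chance of a nominally significant result with no drug effect would be about 10% to 26% instead of 5%. The conclusion also rests on reading the examination and the BSID-III as depending on an examiner's assessment, which is reasonable but not stated in the text.

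**What to change.** In Protocol 5.2 and 5.6:

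- State that the blinding waiver applies to the transfusion endpoints.
- State that, where the usual 2-year examiner does not already know the allocation, it is withheld from that person and from the assessment paperwork until the last 2-year visit. Say that this continues after any earlier unblinding under SAP 4.2, and add a matching sentence there.
- Ask parents not to disclose the allocation to the examiner.
- Record for each child whether the examiner was masked, and report unmasked assessments as such.
- Label the endpoint exploratory throughout, including section 7.1.

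The cost is wording in the protocol and SAP, plus an entry on the visit form. No extra visit or assessor is required, because an assessment by someone who already knows the allocation is reported as unmasked, not repeated. The downside is incomplete masking: parents know the allocation, some will mention it, and some examiners may know it beforehand.
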